## 1. BACKGROUND AND SIGNIFICANCE

Autism spectrum disorder (ASD) is a neurodevelopmental disorder characterized by variable presentation of difficulties with socialization, reciprocal communication, and restrictive/repetitive behaviors [1]. An increasingly higher prevalence of ASD is documented in each successive epidemiological survey and the disorder is now estimated to affect up to 2% of youth in the general population [2]. This rise in prevalence is in part attributed to improved recognition of autism in intellectually capable populations [3].

While there is no established pharmacological treatment for the core features of ASD, there are well-established evidence-based pharmacotherapies available for the management of psychiatric disorders in typically developing individuals that frequently co-occur with ASD.

In general, the psychopharmacologic treatment response in ASD populations is atypically associated with higher susceptibility to adverse effects. Treatment literature suggests that compared to general population, individuals with ASD may be more susceptible to adverse responses to medications [4, 5] [6], and this susceptibility could be dose-related [7].

As individuals with ASD are more susceptible to adverse effects, require lower dose initiation and smaller dose titration, and are often unable to swallow pills due to sensory dysregulation, an approach that requires no medication administration may offer better compliance and tolerability. Given that no empirical evidence on this medication in the referenced population is available, a systematic trial on the efficacy and tolerability of extended-release liquid-formulation MPH for the treatment of ADHD in intellectually capable individuals with ASD is warranted.

Because of the limitations of medication treatment in the approach to ASD related social and cognitive deficits, new treatment approaches are required. We propose a novel treatment approach for social and cognitive deficits based on the use of the Transcranial Photobiomodulation (tPBM). The treatment consists in exposing bilaterally the frontal brain to the tPBM, which may enhance ATP production in affected subjects.

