## 6. SUBJECT SELECTION CRITERIA

### A. Inclusion Criteria

Subjects may be included in the study only if they meet all of the following criteria:

- Male or female participants between 9 and 59 years of age (inclusive)
- Fulfills DSM-5 diagnostic criteria for autism spectrum disorder as established by the clinical diagnostic interview.
- Participants with at least moderately severity of ASD symptoms as demonstrated by SRS raw score  $\geq 85$  and CGI-ASD severity score  $\geq 4$
- Participants must understand the nature of the study. If the participant is under the age of 18, the participant's parent/guardian must sign an IRB-approved informed consent form before initiation of any study procedures. Participants ages 18-59 must sign an IRB-approved informed consent form before the initiation of any study procedures.
- Participants must have a level of understanding sufficient to communicate with the investigator and study coordinator, and to cooperate with all tests and examinations required by the protocol.
- Participant experiencing a major psychiatric disorder will be allowed to participate in the study provided they do not meet any exclusionary criteria.
- Women of child-bearing potential must use a double-barrier method for birth control (e.g. condoms with spermicide) if sexually active.
- The subject is willing to participate in this study.

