### **Study Discontinuation**

We will encourage subjects to continue enrollment in the study via follow-up visits regardless of discontinuation of the tPBM. At the end of the study, we will refer the subjects to their counselor and/or psychiatrist at MGH, and will communicate clinical data upon signed authorization. If the CGI-S increases more than 2 points during the study, the subject will be counseled to start or change to an FDA-approved medication treatment. If the CGI-S increases more than 5 points or if a subject becomes actively suicidal as per clinician judgment, termination from the study will be mandated. If a subject is deemed actively suicidal and is believed to be in imminent danger, the study staff will follow a crisis management plan: keep the subject on the phone and alert a clinician. When the clinician comes to the phone they will assess the situation and determine the appropriate next steps. If the subject is appropriate for outpatient monitoring, the subject will be followed with frequent appointments outside the study. Each subject will have the Investigator's contact information as well as instructions on how to call for emergency services, if needed.

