### **Clinician-Rated Behavioral Measures**

*(Administered biweekly)*

- Clinical Global Impression Scale (CGI; [22]): The CGI is a measure of illness severity, improvement, and efficacy of treatment. The score for severity ranges from 1 (normal, not at all ill) to 7 (among the most extremely ill subjects). Improvement ranges from 1 (very much improved) to 7 (very much worse). The effectiveness index measures to what extent the subject is experiencing therapeutic effects in conjunction with the level of adverse events they are experiencing. CGI scales will be used for the assessment of *ADHD, ASD, anxiety* and *depression*.
- Global Assessment of Functioning Scale (GAF; [23]): composite rating of an individual's overall level of functioning (1= worst to 100 = best).

*(Administered at baseline, midpoint, and endpoint)*

- MGH Social-Emotional Competence Scale [Clinician-Rated Measure] (MGH-SECS-C): This is a 37-item scale that assesses change in the frequency and severity of core and associated symptoms of ASD.
- Hamilton Anxiety Scale (HAM-A; [24]): a rating scale used to assess anxiety. This questionnaire consists of 14 questions assessing these symptoms. Clinicians are asked to rate each symptom as absent, mild, moderate, severe, or very severe.
- Hamilton Depression Scale (HAM-D; [25]): a rating scale used to assess depression. This is a multiple-item questionnaire used to rate the severity of depression in adults. Clinicians are asked to rate each symptom as absent, mild/trivial, moderate or severe.
- Adult ADHD Investigator Symptom Report Scale (AISRS; [26]): The AISRS, shown to be sensitive to drug effects in adult populations, assesses each of the 18 individual criteria symptoms of ADHD in DSM-IV on a severity grid (0=not present; 3=severe; overall minimum score=0; maximum score=54).

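### The CGI-S rise that mandates termination needs a move from 1 to 7, and it cannot occur on CGI-ASD counted from an eligible baseline

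*Combined protocol and SAP*

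**What the plan says.** The Study Discontinuation text in Section 7 sets two score-based tiers.

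- **Counselling:** "If the CGI-S increases more than 2 points during the study, the subject will be counseled" to start or change to an approved medication.
- **Termination:** mandated on either of two grounds, "If the CGI-S increases more than 5 points or if a subject becomes actively suicidal".

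The same text also states: "We will encourage subjects to continue enrollment in the study via follow-up visits regardless of discontinuation of the tPBM".

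The scale is defined in Section 8, Clinician-Rated Behavioral Measures: "The score for severity ranges from 1 (normal, not at all ill) to 7 (among the most extremely ill subjects". The improvement item has its own range: "Improvement ranges from 1 (very much improved) to 7 (very much worse". That section applies CGI scales to four conditions: ADHD, ASD, anxiety and depression. Study Discontinuation does not say which is meant, and it does not say from which visit a rise is counted.

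Section 6.A requires a CGI-ASD severity score of at least 4 for entry. It states no minimum for the other three CGI scales.

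**The concern.** A two-tier rule should give a mild response to moderate worsening and a firm one to severe worsening. Here the firm tier is set so high that almost no path on a seven-point scale leads to it. On the scale for the condition under study, no path from an eligible baseline does. Even the mild tier is barely reachable there: a participant who goes from 5 to 7 on CGI-ASD, the top of the scale, has risen by 2 points and triggers neither action.

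At stake is a safety limit that an ethics board or a participant's parent could take as real protection against marked symptom worsening. The trial enrols from age 9, treatment is self-administered at home, and all visits are virtual, so a stated limit ought to be usable.

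**Working it through.** The protocol gives no derivation for either threshold, so there is no figure to reproduce. The check is arithmetic on the scale.

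**Inputs**
- CGI severity takes whole points from 1 to 7 (Section 8).
- CGI-ASD severity at entry is 4 or more (Section 6.A), taken as still true at week 0.
- Termination: a rise of more than 5, so at least 6 (Study Discontinuation).
- Counselling: a rise of more than 2, so at least 3 (same place).

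**Formula:** largest possible rise = 7 − starting score.

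| Starting score | Largest rise | Termination (≥ 6) reachable | Counselling (≥ 3) reachable |
|---|---|---|---|
| 1 | 7 − 1 = 6 | yes | yes |
| 2 | 7 − 2 = 5 | no | yes |
| 3 | 7 − 3 = 4 | no | yes |
| 4 | 7 − 4 = 3 | no | yes (only 4 to 7) |
| 5 | 7 − 5 = 2 | no | no |
| 6 | 7 − 6 = 1 | no | no |
| 7 | 7 − 7 = 0 | no | no |

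**Results**
- A CGI scale with no entry minimum: termination is reachable from 1 of 7 starting scores, counselling from 4 of 7.
- CGI-ASD from an eligible baseline (4 to 7): termination from 0 of 4, counselling from 1 of 4.

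These count starting scores, not participants. The protocol gives no expected distribution of baseline scores.

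**Other readings**
- *At least 5 instead of more than 5.* This adds only 1 to 6 and 2 to 7. From 4 or more there is still no qualifying move.
- *A week 0 score below the entry minimum.* A score of 3 allows a rise of 4. The stop still needs a reference score of 1.
- *Counted from the lowest score on study.* A participant who entered at 4 or more would have to fall to 1 and then rise to 7. That is possible in principle, but remote.

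**What a workable CGI-ASD severity threshold would be.** A rise of at least 3 is reachable from score 4 only, at least 2 from scores 4 and 5, and at least 1 from scores 4, 5 and 6. No rise is possible from 7. CGI-Improvement has its own 1 to 7 range, so a 6 or 7 can be given at any starting severity.

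**The case against.** The strongest reply is that CGI-ASD may not be the scale meant. The paired action is an approved medication, and Section 1 says that "there is no established pharmacological treatment for the core features of ASD". Medication fits the co-occurring conditions at least as well. Section 6.B excludes people with significant current symptoms of major psychiatric disorders, so low starting scores on those scales are plausible. On that reading the counselling trigger works from scores 1 to 4, and termination is possible from score 1. This stands as far as it goes: the impossibility is specific to CGI-ASD. It does not rescue the stop, which would still need someone rated normal to become among the most extremely ill.

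The second reply is that the score rule is only a backstop. This also largely stands:
- Stops for active suicidality (Study Discontinuation and Section 12) and for mania or hypomania (Section 12) are mandatory.
- Study Discontinuation lets the investigator withdraw a participant for worsening ASD, for a psychiatric disorder, for intolerable adverse effects or on clinical judgment.
- Section 10 allows the dose to be lowered, or the participant dropped, for adverse events.
- Participants are told to report worsening between visits (Section 7, baseline to endpoint), and a clinician can be paged at any hour (Section 10).

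The fallbacks for symptom worsening as such are discretionary, however. None of them supplies a mandatory score-based stop that works.

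Third, the protocol does not state a reference point, so the CGI-ASD impossibility depends on counting from baseline. That is correct. Baseline is the natural choice, because CGIs are listed at the Baseline Visit, but the protocol should say so.

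**Conclusion.** The point holds and is minor. Two things are certain: a rise of more than 5 can be met only by a move from 1 to 7 on any CGI severity scale, and Study Discontinuation names neither the scale nor the reference visit. One thing is conditional: if CGI-ASD is meant or included, and change is counted from a baseline of 4 or more, the mandatory stop cannot occur and counselling is reached only from 4 to 7.

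A reader might infer more than this, and the documents do not support it.
- *That participants have no mandatory stop.* They do, for active suicidality and for mania or hypomania.
- *That the score rule is impossible on every scale.* A move from 1 to 7 remains possible on CGI-ADHD, CGI-Anxiety and CGI-Depression.
- *That the mandated action is wrong.* Termination as the response is a separate design choice, and the unreachable threshold does not call it into question.
- *That the efficacy results are compromised.* The rule does not enter the analysis in Section 9.

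Up to 20 participants are to be exposed. How many would meet a workable threshold cannot be estimated from the documents.

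**What to change.** Revise the Study Discontinuation text as follows.

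1. Name the CGI scale or scales to which each trigger applies.
2. State that change is counted from week 0.
3. Replace the rise of more than 5 points with a stop that eligible starting scores can reach: either a smaller CGI-S rise, or a CGI-Improvement score of 6 or 7 on a named scale. If a CGI-S rise on CGI-ASD is kept, the threshold must be 3 points or fewer to be reachable at all, and no rise is available from a score of 7. CGI-Improvement avoids that ceiling.
4. Keep the counselling trigger milder than the stop. If the stop becomes a rise of 3 or fewer, the present counselling trigger must come down too. The study clinicians should set the cut-offs.

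The mandated action and the suicidality stop can stay as they are.

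**Cost.** Three or four sentences and no new procedure. Table I already has CGIs at weeks 2, 4, 6 and 8, which gives three checks before treatment ends. Section 3, and one sentence in Section 8, describe weekly assessment instead, which would give more.

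**Downsides.** A few participants may be stopped early; that is a judgment, not a calculated figure. Those who leave early are asked for a final assessment, but it is not assured. A lower counselling trigger may lead some to change medication, against the stable-dose rule, and starting one may lead to discontinuation under Concomitant Medications/Treatments. If CGI-ASD-Improvement is the named scale, a primary measure rated open-label also becomes a stopping trigger, which could influence ratings. Shifts among 5, 6 and 7 would not change responder status on that item, where the cut is 2 or less. Whether the consent wording must change cannot be judged, because the consent pages were not available.

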## Photobiomodulation in ASD

A participant may withdraw consent at any time for any reason (e.g., lack of efficacy, adverse events, etc.). A subject may be withdrawn from the study at any time if any of the following conditions are met:

- Worsening of ASD or current/emergent major psychiatric disorder.
- Subjects who experience intolerable adverse effects as determined by the PI.
- Emergent suicidality
- Pregnancy
- Failure to keep study appointments for more than 2 consecutive visits
- Clinical judgment of the investigator

Those subjects who terminate study participation before the completion of the study will be asked to complete all tasks scheduled to take place on the final study visit at the time of study discontinuation.

Subjects may receive three clinical follow-up visits at the completion of the study (or if they are required to discontinue for safety reasons), allowing adequate time for appropriate psychiatric referrals to treaters in their communities. Follow-up visits are optional and are at no cost to participants. These visits are not part of the clinical trial and no research data will be collected during follow-up. Subjects who fail to keep study appointments, or are non-compliant may be dropped from the study. These study subjects will be given a referral to treaters in their area but will not be offered three follow-up visits.

If a subject would like us to forward their clinical history to his/her primary care physician, or a new clinician, we will forward any pertinent information with the proper completed release of information authorization form. If a subject who has come from the clinic of the investigator happens to drop out of the study, he or she will return to his or her treating physician.

### **8. ASSESSMENTS (See Table I for an assessment schedule)**

Subjects will be evaluated at biweekly intervals. At each weekly visit, measures of safety and efficacy will be obtained using assessments of psychiatric symptoms and functioning (CGIs, GAF) and measures of adverse effects (CTAE). Additionally, height and weight will be collected during the screening evaluation (week 99) and the final study visit (week 8 or endpoint).-At the midpoint (end of week 4) and final study visits (Week 8 or Endpoint), additional clinician- and subject-rated assessments will be repeated (see below for details). Optional observer-rated assessments will be completed at the baseline (week 1) and final study visits.

All data will be collected and entered into REDCap. REDCap is an electronic data capture system that streamlines data collection and ensures data integrity. REDCap software allows researchers to design and implement study surveys electronically for collecting, storing, retrieving, and manipulating data. Participants will be sent the RedCap link via encrypted email. The link will not allow the participant to access any other data stored on the password-protected database. Only those subjects who receive the link via email will be able to access the questionnaires. The responses will then be transmitted securely via an encrypted connection and stored in a secured database. Electronic data capture eliminates the need for subsequent data entry by staff, thus minimizing human error. However, in the event that REDCap is

malfunctioning, study staff will print all study instruments and study data will be collected in paper form.

### **Clinician-Rated Diagnostic Assessments**

*(Administered at screening evaluation)*

- MGH Autism Spectrum Disorder DSM-5 Diagnostic Symptom Checklist (MGH-ASD-SCL): The range and severity of subjects' ASD symptoms will be assessed with the clinician-administered MGH-ASD-SCL. This screening instrument adopted items from DSM-5 diagnostic criteria for ASD and assesses for the individual core domains and associated features of ASD.

### **Clinician-Rated Behavioral Measures**

*(Administered biweekly)*

- Clinical Global Impression Scale (CGI; [22]): The CGI is a measure of illness severity, improvement, and efficacy of treatment. The score for severity ranges from 1 (normal, not at all ill) to 7 (among the most extremely ill subjects). Improvement ranges from 1 (very much improved) to 7 (very much worse). The effectiveness index measures to what extent the subject is experiencing therapeutic effects in conjunction with the level of adverse events they are experiencing. CGI scales will be used for the assessment of *ADHD, ASD, anxiety* and *depression*.
- Global Assessment of Functioning Scale (GAF; [23]): composite rating of an individual's overall level of functioning (1= worst to 100 = best).

*(Administered at baseline, midpoint, and endpoint)*

- MGH Social-Emotional Competence Scale [Clinician-Rated Measure] (MGH-SECS-C): This is a 37-item scale that assesses change in the frequency and severity of core and associated symptoms of ASD.
- Hamilton Anxiety Scale (HAM-A; [24]): a rating scale used to assess anxiety. This questionnaire consists of 14 questions assessing these symptoms. Clinicians are asked to rate each symptom as absent, mild, moderate, severe, or very severe.
- Hamilton Depression Scale (HAM-D; [25]): a rating scale used to assess depression. This is a multiple-item questionnaire used to rate the severity of depression in adults. Clinicians are asked to rate each symptom as absent, mild/trivial, moderate or severe.
- Adult ADHD Investigator Symptom Report Scale (AISRS; [26]): The AISRS, shown to be sensitive to drug effects in adult populations, assesses each of the 18 individual criteria symptoms of ADHD in DSM-IV on a severity grid (0=not present; 3=severe; overall minimum score=0; maximum score=54).

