### Secondary Objectives:

- To assess the *safety and tolerability* of the Transcranial Photobiomodulation in patients with Autism Spectrum Disorder across the lifespan
- To study the treatment effect of Transcranial Photobiomodulation on mood, social cognition, executive function, ADHD, depression and anxiety symptoms in adults with Autism Spectrum Disorder

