### **3. LENGTH OF STUDY**

This study will last up to 12 weeks from enrollment (allowing up to four weeks from the date of consent to schedule and complete the initial screening process). Once subjects have completed the screening process and baseline characterization, they will begin the 8-week open-label trial. Subjects will be assessed on measures of efficacy and safety every week throughout the study.

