### **Washout Period**

After the screening period, subjects who are currently taking prohibited medications as noted in exclusion criteria, and willing to discontinue the use of their medication may do so in order to be eligible for participation in this study, if clinically appropriate per clinician judgment. If

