## Photobiomodulation in ASD

appropriate, medication washout will be recommended by our clinicians to participants and current providers. Clinicians will determine a washout schedule based on the half-life of the medication, the adverse effects associated with treatment and withdrawal, and an assessment of individual factors including duration on drug and dose. No subjects will be asked to discontinue ongoing exclusionary medications to participate in the study; however, if the subject is already tapering the medication off for clinical reasons at the time of screening and evaluation for participation, they will be considered eligible to participate only after the washout period as described. Our office does not take over care for the patient, but remains available during this time period. The washout schedule will be discussed with the participant and current providers.

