At the baseline visit, the subject will be examined via a video call to inspect the sites of application (left and right forehead) for any possible skin lesions (e.g. laceration or signs of inflammation) which would contraindicate the treatment. The subject will then be instructed on appropriate administration of tPBM. The treatment device is classified as an “Exempt” device in accordance with the requirements of the international standard EN 62471 – Photobiological safety of lamps and lamp systems and, when used correctly, the output is less than the maximum permissible exposure (MPE) no special controls are needed for the environment it is to be used in. At the time of study implementation, the staff will be provided training on basic safety procedures relative to the use of the device. The staff will then instruct the subject on the administration of the tPBM with careful observation that the subject appropriately places the headband device. For subjects ages 9-17, the delivery of the tPBM is expected to last 10-40 minutes total (simultaneous application on the left and right forehead). The subject will be asked to rest for five minutes after the delivery of tPBM. Sites of application will be inspected at each study visit. Subjects will be instructed to administer the treatment sessions daily for eight weeks, with each session lasting 10-40 minutes. Subjects will be instructed to contact the investigator or a member of his staff at any time between visits concerning adverse events or worsening of symptoms. Subjects ages 18-59 will be instructed to administer the treatment sessions daily for eight weeks, with each session lasting 20-50 minutes. Subjects will be instructed to contact the investigator or a member of his staff at any time between visits concerning adverse events or worsening of symptoms.

The following assessments will be performed at the Baseline Visit:

- CGIs

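### Section 8 and Table I disagree on whether HAM-A, HAM-D and AISRS are rated at week 0; if Table I is followed, the change on these three secondary scales includes untreated time

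*Combined protocol and SAP*

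**What the plan says.** **Section 8, Clinician-Rated Behavioral Measures.** Four scales (MGH-SECS-C, HAM-A, HAM-D and AISRS) stand under one timing line: "Administered at baseline, midpoint, and endpoint". The heading of Section 8 refers the reader to Table I for the schedule.

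**Table I.** MGH-SECS-C is marked at weeks 0, 4 and 8. HAM-A, HAM-D and AISRS are marked at weeks 99, 4 and 8, with an empty week-0 cell.

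**Section 7, Study baseline to Endpoint.** The list introduced by "The following assessments will be performed at the Baseline Visit" names the CGIs, GAF, CTAE, concomitant medications, ADHD-SC and BRIEF-A/P. It does not name HAM-A, HAM-D or AISRS.

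**Section 3.** The overall limit reads "This study will last up to 12 weeks from enrollment". The part of that limit set aside before treatment is described as "allowing up to four weeks from the date of consent to schedule and complete the initial screening process". After screening and baseline characterization, "they will begin the 8-week open-label trial".

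**Section 7, Washout Period.** Washout comes later than screening: "After the screening period, subjects who are currently taking prohibited medications as noted in exclusion criteria" may stop them if clinically appropriate. The section adds that nobody will be asked to stop an exclusionary medication. Of those already tapering for clinical reasons it says that "they will be considered eligible to participate only after the washout period as described". No maximum length is given.

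**Section 2, Secondary Objectives.** One objective is "To study the treatment effect of Transcranial Photobiomodulation on mood, social cognition, executive function, ADHD, depression and anxiety symptoms in adults with Autism Spectrum Disorder". Section 7 lists HAM-A, HAM-D and AISRS among the secondary outcome measures for it.

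**Section 9.** The analysis pairs each participant's pre-treatment baseline with the last assessment, using Wilcoxon signed rank tests for scale scores. It does not tie baseline to week 99 or week 0.

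**The concern.** There is no control group, so everything the study says about HAM-A, HAM-D and AISRS rests on a before-and-after difference. The before value should therefore be taken as close to the first session as possible. Any drift between the rating and the first session enters the difference and cannot be separated from treatment. Section 9 accepts that influences changing over time can still bias the comparison, and sets this aside because the trial is short. A screening-based starting value lengthens the very interval on which that argument rests.

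There is also a question of comparability. Section 7 pairs HAM-A with CGI-Anxiety, HAM-D with CGI-Depression, and AISRS with the ASRS and CGI-ADHD. Under Table I the members of each pair can start from different visits, so a disagreement between them could reflect timing rather than the instrument. A week-0 rating that was never taken cannot be recovered afterwards.

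**Working it through.** **Step 1. Does the conflict exist?** Table I has eight visit columns (99, 0, 1, 2, 3, 4, 6, 8), and each row below reads cleanly into eight cells.

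| Scale | Section 8 timing | Table I marks |
|---|---|---|
| MGH-SECS-C | baseline, midpoint, endpoint | 0, 4, 8 |
| HAM-A | same line | 99, 4, 8 |
| HAM-D | same line | 99, 4, 8 |
| AISRS | same line | 99, 4, 8 |
| CGIs | biweekly | 99, 0, 2, 4, 6, 8 |
| ASRS (18+) | baseline, midpoint, final | 0, 4, 8 |
| SRS-2 (self/informant) | self: baseline, midpoint, final; informant: baseline, endpoint | 99, 0, 4, 8 |

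The MGH-SECS-C row shows that baseline in that Section 8 line corresponds to week 0. The three scales in question are the only efficacy scales in Table I without a week-0 mark. The SRS-2 and the CGIs carry both a screening and a week-0 mark, so a screening rating does not by itself replace the baseline one elsewhere in the table.

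**Step 2. What gap do the documents allow?** The plan's own total is reproduced: 4 weeks (screening allowance) + 8 weeks (treatment) = 12 weeks. The most pre-treatment time within that total is 12 − 8 = 4 weeks. The four weeks run from consent to completed screening. They are not a stated interval from the HAM-A, HAM-D or AISRS rating to the first session, so the gap g is an assumption. It could be near 0, it reaches at most 4 weeks within the 12-week total, and it could exceed 4 if washout followed a full screening period.

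**Step 3. Untreated share of the change interval, if Table I is followed.** Share = g / (g + t), where t is the number of weeks on treatment at the later rating.

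| Gap g (weeks, assumed) | To week 8: g/(g+8) | To week 4: g/(g+4) |
|---|---|---|
| 1 | 1/9 = 11% | 1/5 = 20% |
| 2 | 2/10 = 20% | 2/6 = 33% |
| 3 | 3/11 = 27% | 3/7 = 43% |
| 4 | 4/12 = 33% | 4/8 = 50% |

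With a rating at week 0, g = 0 and both shares are 0%.

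These are shares of calendar time, not of the score change. The documents give no drift rate or standard deviation for these scales, so the bias in points cannot be computed.

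**The case against.** The strongest reply is that Section 8 already asks for a baseline rating and Section 9 speaks of a baseline before treatment, so the intended design may be sound and Table I may simply be wrong. That stands in part. No sentence says Table I overrides the text, so a reader who infers that a screening-only rating is the settled design goes further than the documents do. What remains is that Section 8 itself sends staff to Table I, and the two cannot both be followed.

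Other stronger readings are also tempting and are not supported:

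- *That the rating is taken four weeks before irradiation.* Four weeks is a ceiling inferred from the consent-to-screening allowance.
- *That medication change contaminates the scales generally.* The exclusion criteria require any continued psychotropic to be at a stable dose for at least 4 weeks before study treatment, and the concomitant-medication rules require stability during the trial. Withdrawal matters only for those who wash out or taper after screening, a subset of unknown size that may be empty.
- *That the depression, anxiety and ADHD results as a whole are affected.* CGI-Depression, CGI-Anxiety, CGI-ADHD and the adult ASRS have week-0 marks, as does the primary SRS-2.
- *That the baseline-visit list confirms Table I.* That list also omits MGH-SECS-C, SRS-2, ASRS and Q-LES-Q, all marked at week 0, and it names ADHD-SC, which Table I does not contain. The screening list in Section 7 does not name the three scales either. Neither list settles the matter.

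It is also fair to say that drift between week 0 and week 8 remains in any uncontrolled study. A week-0 rating removes only the pre-treatment part, but that part is avoidable.

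**Conclusion.** The conflict between Section 8 and Table I is certain, and so is the absence of a defined baseline visit in Section 9. The bias is conditional: it arises if Table I is what is carried out. In that case the paired change on HAM-A, HAM-D and AISRS contains untreated time. Under an assumed gap of 1 to 4 weeks, with no added washout, this is between about a ninth and a third of the interval to week 8, and between a fifth and a half of the interval to week 4. For anyone who tapers after screening, the change also contains the effect of withdrawal, and the gap may be longer.

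The reach is limited to three secondary scales in a small single-group pilot, and the primary outcome is not touched. The point still deserves correction before further participants are rated, because the missing value cannot be recovered and the remedy is small.

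**What to change.** 1. In Table I, mark HAM-A, HAM-D and AISRS at week 0, before the first session, to match Section 8. The screening rating may be kept as well, as is done for the CGIs; nothing needs to be deleted.
2. Bring the baseline-visit list in Section 7 into line with every measure that Table I places at week 0, not only these three, and settle whether ADHD-SC belongs in it.
3. State in Section 9 that the week-0 value is the baseline for the paired comparison.

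The cost is one table edit, one list edit and one sentence, plus a slightly longer week-0 visit for the clinician and participant. No visit is added.
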